APPENDIX VIIIb: FREQUENCY OF ITCHING DUE TO ATOPIC DERMATITIS EXAMPLE

Frequency of Pruritus

Select the number that best describes frequency of itching due to atopic dermatitis over the past 24 hours (check one number only).

										
0	1	2	3	4	5	6	7	8	9	10
Never /No itching									Always/constant itching	

APPENDIX IX: SCORING ATOPIC DERMATITIS (SCORAD) EXAMPLE

Area (A)

To determine extent, the sites affected by eczema are shaded on a drawing of a body. The [REDACTED] is used to calculate the affected area (A) as a percentage of the whole body ([Appendix II](#)).

Body area	Extent	Maximum
Head and neck		9%
Upper limbs		9% each
Lower limbs		18% each
Anterior trunk		18%
Back		18%
Genitals		1%
Total (A):		100%

Add the scores for each area. The total area is 'A', which has a possible maximum of 100%.

Intensity (B)

A representative area of eczema is selected. In this area, the intensity of each of the following signs is assessed as none (0), mild (1), moderate (2) or severe (3).

- Redness
- Swelling
- Oozing/crusting
- Scratch marks
- Skin thickening (lichenification)
- Dryness (this is assessed in an area where there is no inflammation)

The intensity scores are added together to give 'B' (maximum 18).

Representative Area of Eczema					
Redness	Swelling	Oozing/crusting	Scratch marks	Skin thickening (lichenification)	Dryness (this is assessed in an area where there is no inflammation)
 0 (None)					
 1 (Mild)					
 2 (Moderate)					
 3 (Severe)					

Subjective symptoms (C)

Subjective symptoms (itch and sleeplessness), are each scored by the patient or relative using a visual analogue scale where 0 is no itch (or no sleeplessness) and 10 is the worst imaginable itch (or sleeplessness). These scores are added to give 'C' (maximum 20).

SCORAD	=	A/5	+	7B/2	+	C
	=		+		+	

The maximum score is 103.

Subjective symptoms (C)

Note: Please ensure that the line is 100 mm in length after printing the source document and measuring the distance

Instructions for the subject

Itch:

No itch

Worst imaginable itch

Sleeplessness:

No sleeplessness

Sleeplessness

APPENDIX X: PROTOCOL FOR ORTHOSTATIC (POSTURAL) VITAL SIGN MEASUREMENT EXAMPLE

Procedure¹⁴

1. Assess by verbal report and observation the subject's ability to stand.
2. Have subject lie in bed with the head flat for a minimum of 5 minutes.
3. Measure the blood pressure and the pulse while the subject is supine.
4. Instruct subject to stand.
 - Ask subject about dizziness, weakness, or visual changes associated with position change. Note diaphoresis or pallor.
 - If subject is unable to stand, sit patient upright with legs dangling over the edge of the bed.
 - The subject should be permitted to resume a supine position immediately if syncope or near syncope develops.
5. Measure the blood pressure and pulse measurements 2-5 minutes after subject stands. Support the forearm at heart level when taking the blood pressures to prevent inaccurate measurement.
6. Assist subject back to bed in a position of comfort.
7. Document vital signs and other pertinent observations. Note all measurements taken and the position of the subject during each reading.
8. Report all findings, including all sets of blood pressure and pulse results, and whether the subject experienced pallor, diaphoresis, or faintness when upright, to the independent safety assessor

Pre-dose Post-dose

subject's position	pulse rate* (bpm)	systolic BP(mmHg)	diastolic BP (mmHg)	observations associated with position change	Evaluation (change +/- from supine values)
Supine (after the Subject is rested for at least 5 minutes)					
decline of ≥ 20mm Hg in systolic BP = orthostatic hypotension decline of ≥ 10mm Hg in diastolic BP = orthostatic hypotension increase of at least 30bpm in pulse rate may suggest hypovolemia

2-5 minutes after subject stands				 dizziness  weakness  visual changes  diaphoresis  pallor  other:	change (+/-) in pulse rate (bpm): _____ change (+/-) in systolic BP (mmHg) : _____ change (+/-) in diastolic BP (mmHg) : _____  orthostatic hypotension  suggested hypovolemia

* Pulse rate to be measured by counting the number of heart beats over 60 seconds (the pulse rate should not be extrapolated after counting for part of 60 seconds).

If needed, at the independent safety assessor's discretion, pulse rate and BP may be measured in triplicate (at 1-2 minute intervals). Report the lowest value.

6.12.8	Ophthalmological Examination	35
6.12.9	Dose [REDACTED] Monitoring	35
7.	TIMING OF ANALYSES	36
8.	CHANGES FROM PROTOCOL-SPECIFIED ANALYSES	36
9.	LIST OF PLANNED TABLES, FIGURES, AND LISTINGS	37
10.	LITERATURE CITATIONS / REFERENCES.....	37
11.	APPENDICES	38
11.1	Study visit Schedule - all subjects not at a higher risk of bradyarrhythmia.....	38
11.2	Study visit Schedule - subjects at a higher risk of bradyarrhythmia.....	45

LIST OF ABBREVIATIONS

Abbreviation	Explanation
ACLS	Advanced Cardiac Life Support
AD	Atopic dermatitis
AE	Adverse Event
ALC	Absolute Lymphocyte Counts
ALP	Alkaline Phosphatase
ALT	Alanine Aminotransferase
ANC	Absolute Neutrophil Count
AUC ₀₋₆	Area under the concentration-time curve up to 6 hours
AUC _{0-last}	Area under the concentration-time curve up to the last observed quantifiable concentration
aPTT	Activated Partial Thromboplastin Time
AST	Aspartate Aminotransferase
ATWC	Active Treatment Worst Case
AV block	Atrioventricular block
BLQ	Below Limit of Quantification
BMI	Body Mass Index
BSA	Body Surface Area
C _{max}	Maximum concentration
CMH	Cochran-Mantel-Haenszel
COPD	Chronic Obstructive Pulmonary Disease
CRA	Clinical Research Associate
CRO	Contract Research Organization
C _{trough}	Lowest concentration reached by a drug before the next dose
CV	Coefficient of Variation
DLQI	Dermatology Life Quality Index
DSMB	Data Safety Monitoring Board
EASI	Eczema Area and Severity Index
ECG	Electrocardiogram
eCRF	Electronic Case Report Form
EOT	End of Treatment
FEV	Forced Expiratory Volume
FVC	Forced Vital Capacity
GGT	Gamma Glutamyltransferase
HBsAg	Surface Antigen of The Hepatitis B Virus (HBV)
hCG	Human Chorionic Gonadotropin
HCV	Hepatitis C Virus
HDL	High-Density Lipoproteins
HEENT	Head, Eyes, Ears, Nose and Throat
HIV	Human Immunodeficiency Virus
INR	International Normalized Ratio

ITT	Intent to Treat
LDL	Low-Density Lipoprotein
LLN	Lower Level of Normal
LOCF	Last Observation Carried Forward
LS	Least Squares
MCV	Mean Corpuscular Volume
MedDRA	Medical Dictionary for Regulatory Activities
MM	Medical Monitor
MMRM	Mixed Model for Repeated Measures
OCT	Optical Coherence Tomography
PD	Pharmacodynamic
PFT	Pulmonary Function Tests
PGIC	Patient Global Impression of Change
PGIS	Patient Global Impression of Severity
PK	Pharmacokinetics
PML	Progressive Multifocal Leukoencephalopathy
POEM	Patient Oriented Eczema Measure
PP	Per Protocol
PP-NRS	Peak Pruritus Numeric Rating Scale
PRES	Posterior Reversible Encephalopathy Syndrome
PT	Prothrombin Time
QRS	A combination of the Q wave, R wave and S wave
QT	QT Interval (the time from the start of the Q wave to the end of the T wave)
QTcF	QT Corrected by Fridericia's Formula
S1P	Sphingosine-1-Phosphate
SAP	Statistical Analysis Plan
SCORAD	SCORing Atopic Dermatitis
SUSAR	Suspected Unexpected Serious Adverse Reactions
TEAE	Treatment Emergent Adverse Event
t_{max}	Time to maximum concentration
VAS	Visual Analogue Scale
vIGA	validated Investigator's Global Assessment
VZV	Varicella Zoster Virus
WBC	White Blood Cells

1. INTRODUCTION

The purpose of this statistical analysis plan (SAP) is to provide details of the statistical analyses that have been outlined within the protocol "A Randomized, Double-Blind, Placebo-Controlled Study to Assess the Efficacy and Safety of SCD-044 in the Treatment of Moderate to Severe Atopic Dermatitis", version 3.0, dated April 10, 2023.

Sun Pharmaceutical Industries Ltd. is developing a Sphingosine 1-phosphate (S1P) receptor agonist, SCD-044, to treat moderate to severe atopic dermatitis. The current study is a Phase IIb dose ranging study to assess the efficacy and safety of SCD-044 in the treatment of moderate to severe atopic dermatitis (AD).

2. OBJECTIVES AND ESTIMANDS

2.1 Primary Objective

The primary objective of this study is to determine the effect of SCD-044 treatment on moderate to severe atopic dermatitis, as measured by proportion of subjects showing at least 75% improvement in Eczema Area and Severity Index (EASI) at Week 16.

2.2 Primary Estimand

The primary estimand is defined as follows:

Population of interest	Subjects with moderate to severe atopic dermatitis
Outcome Measure/Endpoint	Achieving at least 75% improvement in EASI at Week 16
Treatment	SCD-044 [REDACTED] and [REDACTED] mg once daily
Intercurrent Event	Use of rescue medication (systemic or topical), use of prohibited medications (as determined during blinded data review) and early treatment discontinuation. Composite strategy will be applied to these intercurrent events and the subjects with intercurrent events will be treated as non-responders.
Population-level Summary Measure	Difference in proportions between each the active treatment arms and placebo arm

2.3 Secondary Objectives

The secondary objectives of this study are:

- To evaluate the efficacy of SCD-044 as measured by validated Investigator's Global Assessment (vIGA) of disease severity
- To evaluate the efficacy of SCD-044 as measured by Peak Pruritus Numeric Rating Scale (PP-NRS)
- To evaluate the efficacy of SCD-044 as measured by SCORing Atopic Dermatitis (SCORAD)

- To evaluate the efficacy of SCD-044 as measured by Patient Oriented Eczema Measure (POEM)
- To evaluate the efficacy of SCD-044 as measured by change in body surface area (BSA) involvement over the treatment period
- To assess the effect of SCD-044 on quality of life, as measured by Dermatology Life Quality Index (DLQI)
- To assess the effect of SCD-044 on Patient Global Impression of Severity (PGIS)
- To assess the effect of SCD-044 on Patient Global Impression of Change (PGIC)
- To assess the safety and tolerability of SCD-044 in subjects with moderate to severe atopic dermatitis
- [REDACTED]

2.4 Key secondary estimand

The key secondary estimand is defined similar to the primary estimand as follows:

Population of interest	Subjects with moderate to severe atopic dermatitis
Outcome Measure/Endpoint	Achieving a vIGA of '0' or '1' with at least 2-point reduction from baseline at Week 16
Treatment	SCD-044 [REDACTED], [REDACTED] and [REDACTED] mg once daily
Intercurrent Event	Use of rescue medication (systemic or topical), use of prohibited medications (as determined during blinded data review) and early treatment discontinuation. Composite strategy will be applied to these intercurrent events and the subjects with intercurrent events will be treated as non-responders.
Population-level Summary Measure	Difference in proportions between each the active treatment arms and placebo arm

2.5 Exploratory Objectives

The exploratory objectives of this study are:

- [REDACTED]
- [REDACTED]
- [REDACTED]
- [REDACTED]

3. STUDY OVERVIEW

3.1 Study Design

Subjects in this randomized, double-blind, placebo controlled, parallel-group, multiple-center study will be assigned to treatment with the investigational products or placebo control according to a randomization scheme and [REDACTED] schedule.

- **Part I** (16 weeks): Subjects will be randomized to Placebo, Low dose ([REDACTED] mg), Intermediate dose ([REDACTED] mg) or High dose ([REDACTED] mg) of SCD-044 in 3:1:1:3 ratio

[REDACTED] to assess primary and secondary endpoints at 16 weeks.

- [REDACTED]
- [REDACTED]

Statistical Analysis Plan
Study Code SCD-044-19-16

Version Final

Date Jan 21, 2025

- [REDACTED]
- [REDACTED]
- [REDACTED]

Phone or in person contacts may be scheduled for visits [REDACTED] visits to collect information on concomitant medication, compliance with the study drug use, health changes (AEs & AESI), queries for PML and PRES and to provide instructions.

[REDACTED]

[REDACTED]

[REDACTED]

Subjects will be admitted into the study after informed consent has been obtained. An Unscheduled Visit is allowed at any time, for any reason, if in the Investigator's opinion it is warranted. If a Subject is discontinued from the study during an Unscheduled Visit, the Unscheduled Visit will be referred to as an Early Discontinuation Visit and all procedures scheduled for Early Discontinuation will be performed. If the Unscheduled Visit is not an Early Discontinuation Visit (i.e., the Subject will continue to take part in the study), then all procedures scheduled for that Unscheduled Visit will be performed. Subjects who are discontinued early from the study must attend the Follow-up visit 4 weeks after the date of Early Discontinuation.

If necessary due to the COVID-19 pandemic, Visit 18 may have assessments done at home or remote visit. Remote visits must be discussed and consulted with the CRO's and the Sponsor's medical monitor before planning. Scheduled blood collection (for these visits only) may be waived if the individual subjects have not had a clinically significant changes or undesired trend in lab or chemistry values prior to visit 15. Remote assessments or delayed visit 18 will be recorded in the source documents and noted as a minor protocol deviation.

COVID-19 related protocol deviations will be analyzed to assess whether a protocol amendment or other modifications are needed. The Sponsor together with investigators plan to assess the COVID-19 situation to evaluate the benefit: risk of the study on an ongoing basis.

Changes in study visit schedules, missed visits, or subject discontinuations may lead to missing information (e.g., for protocol-specified procedures). It is important to capture specific information in the subject records that explains the basis of the missing data, including the relationship to COVID-19, for missing protocol-specified information (e.g., from missed study visits or study discontinuations due to COVID-19).

A subset of eligible subjects will participate in photographic evaluation.

Randomization and re-randomization will be stratified by three factors: [REDACTED] Approximately the same number of male and female subjects will be enrolled between treatment groups. [REDACTED] . Approximately the same number of subjects who have prior exposure to biologics therapy for atopic dermatitis will

[figure not shown]
be enrolled between treatment groups.

[figure not shown]
[figure not shown]
The assigned Investigational Product will be administered orally once a day. Subjects will be required to use diaries to document the date of study treatments, any missed treatments, and the occurrence of all adverse events.

The duration of each Subject's participation in the study will be approximately 40 weeks (280 days).

If the Principal Investigator or designee determines that the Subject's condition has worsened to the degree that it is unsafe for the Subject to continue in the study, the Subject may be discontinued from the study as a treatment failure and the Subject may be treated using the standard care.

Subjects with conditions or treatments that may affect cardiovascular safety (e.g. heart rate less than 55 bpm), history of uveitis or history of pulmonary conditions such as active severe respiratory disease (e.g. COPD, tuberculosis or pulmonary fibrosis, severe asthma or asthma requiring regular treatment with oral steroids) will be excluded due to the known mechanism-based AEs within this class which may expose such subjects to unwarranted excess risk for a condition with available alternatives.

3.3 Randomization and Unblinding Procedures

In order to maintain the study blind the randomization schedule will be generated by a third party. Randomization will be performed according to a computer-generated randomization scheme.

- [REDACTED]
- [REDACTED]
- [REDACTED]

- [REDACTED]
- [REDACTED]

- [REDACTED]
- [REDACTED]
- [REDACTED]
- [REDACTED]
- [REDACTED]
- [REDACTED]

4. STUDY ENDPOINTS/OUTCOMES

4.1 Primary endpoint

The primary endpoint of this study is the proportion of subjects who achieve $\geq 75\%$ overall improvement in EASI score from Baseline to Week 16.

4.2 Key secondary endpoint

Key secondary endpoint of this study is the proportion of subjects who achieve score of '0' (clear) or '1' (almost clear) on a 5-point, vIGA scale and ≥ 2 point reduction from Baseline to Week 16.

4.3 Other secondary endpoints

The other (non-key) secondary endpoints of this study are:

[REDACTED]

- Proportion of subjects who achieve ≥ 4 -point or ≥ 3 -point improvement in PP-NRS from Baseline to Week [REDACTED], and 32
- [REDACTED]
- Proportion of subjects who achieve SCORAD 50 and SCORAD 75 response from Baseline to Week [REDACTED] 32
- Change from Baseline in quality of life measured by DLQI scores to Weeks [REDACTED] 32
- Proportion of subjects who achieve DLQI total score 0 or 1 at Weeks 16 and 32
- [REDACTED]
- Change from Baseline in percent BSA with atopic dermatitis measured to Weeks [REDACTED]
- Change from Baseline in POEM score to Weeks [REDACTED] 32
- Proportion of subjects who achieve ≥ 4 -point improvement from Baseline in the frequency of itching recorded in PP-NRS to Weeks [REDACTED] 32
- Proportion of subjects with improvement in PGIC from Baseline to Weeks [REDACTED] and 32
- Change in PGIS of disease from Baseline to Weeks [REDACTED] 32

4.4 Exploratory endpoints

Exploratory endpoints include:

5. ANALYSIS POPULATIONS

5.1 Safety Population

The Safety Population will consist of all subjects who were randomized into the study and dispensed study drug. This population will be the primary population for the safety analysis. Subjects will be analyzed according to the actual treatment received.

5.2 Intent-to-Treat (ITT) Population

The Intent-to-Treat (ITT) Population will consist of all randomized subjects regardless of whether they received the investigational product. This population will be the main population for the efficacy analyses. Subjects will be analyzed according to the treatment they were randomized to receive.

5.3 Per-Protocol (PP) Population

The Per-Protocol (PP) Population will consist of all ITT subjects who meet all inclusion/exclusion criteria, complete part 1 of the study, and have no protocol violations that affect proper administration of the treatment or accurate evaluation of its effectiveness. For more information on protocol violations see section 6.7. This population will be the supportive population for the efficacy analyses. Subjects will be analyzed according to the treatment they were randomized to receive.

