9.5 Datasets to be Analyzed

Three analysis populations will be used in the analysis of the clinical data:

1. A Safety Population subject is any individual who was randomized into the study and dispensed study drug.
2. The ITT Population includes all randomized subjects regardless of whether they received the investigational product.
3. The Per Protocol (PP) Population includes all ITT subjects who meet all inclusion/exclusion criteria and have no protocol violations that affect proper administration of the treatment or accurate evaluation of its effectiveness.

Additionally, the Screen Fail subjects will be summarized, including reasons for removal.

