9.8 Efficacy Assessment

Primary endpoint:

- Proportion of subjects who achieve $\geq 75\%$ overall improvement in EASI score from Baseline to Week 16

Key Secondary endpoint:

- Proportion of subjects who achieve score of '0' (clear) or '1' (almost clear) on a 5-point, vIGA scale [REDACTED] Week 16

Other Secondary endpoints:

- Percent change in EASI score from Baseline to Week [REDACTED] 32
- [REDACTED]
- [REDACTED]
- [REDACTED]
- [REDACTED]
- [REDACTED]
- Change in mean EASI score from Baseline to Week [REDACTED] 32
- [REDACTED]
- [REDACTED]
- [REDACTED]
- Proportion of subjects who achieve ≥ 4 -point improvement in PPI-NRS from Baseline to Week [REDACTED] 32
- [REDACTED]
- [REDACTED]
- Proportion of subjects who achieve SCORAD 50 and SCORAD 75 response from Baseline to Weeks [REDACTED] 32
- [REDACTED]
- Change from Baseline in quality of life measured by DLQI scores to Week [REDACTED]
- [REDACTED]
- [REDACTED]
- Change from Baseline in percent BSA with atopic dermatitis measured to Week [REDACTED] 32
- Change from Baseline in POEM score to Week [REDACTED] 32

- Change in PGIS of disease from Baseline to Week [REDACTED] 32

Efficacy Analysis

The primary and key secondary efficacy variables will be analyzed using a [REDACTED] test, [REDACTED] using the Intent-to-Treat (ITT) Population. Additional details will be included in the SAP.

Sensitivity Analyses

For sensitivity testing, the primary and key secondary endpoints analyses will also be performed using the per protocol (PP) population.

Additional sensitivity analyses will be performed for the primary efficacy variable using the following populations:

- The Intent-to-Treat (ITT) Population using Last-Observation-Carried-Forward imputation (LOCF)
- The Per Protocol (PP) Population, using Observed Cases (OC)
- The Intent-to-Treat (ITT) Population, active treatment worst case (ATWC), defined as all missing assessments in the placebo group defaulted to responder but missing assessments in active treatment arm defaulted to nonresponder. Full tipping point analysis methods will be discussed in the SAP.

Additional details of the statistical approach will be provided in the statistical analysis plan.

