6.2 Subject Disposition

Disposition will be summarized for Part I, Part II, and the study overall.

For Part I, the number of subjects who were screened, were screen failures, were randomized to treatment, included in the Safety, ITT, and PP, completed Part I (i.e., attended Week 16 visit) and prematurely discontinued from the study during Part I (along with the reasons for discontinuation) will be presented.

For Part II, the summary will present the number and percentage of subjects who were re-randomized for Part II, completed Part II (i.e., attended Week 32 visit) and prematurely discontinued from the study during Part II (along with the reasons for discontinuation).

For the study overall, the summary will present the number of subjects who were screened, were screen failures, were randomized to treatment, included in the Safety, ITT, and PP, attended the visits at Weeks 16 and 32, completed the study (week 36) and prematurely discontinued from the study at any time (along with the reasons for discontinuation).

Subjects who discontinued from the study for reasons related to the COVID-19 pandemic will be identified through manual review. Their number and percentage will be summarized separately.

Number and percentage of subjects who did not attend a visit for reasons related to COVID-19 will be provided by visit and treatment group.

All disposition information will be listed. Also, a listing of enrollment details will provide the date of informed consent and inclusion/exclusion criteria not met, if any.

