6.9.1.3 Supplementary analyses

The following supplementary analyses will be performed:

1. Analysis similar to the primary analysis, but on the Per Protocol population using observed cases only with no imputations.
2. Analysis similar to the primary analysis, but on the ITT population excluding the subjects with protocol deviations related to the COVID-19 pandemic. This analysis will be performed only if more than 5% of subjects have protocol deviations related to the COVID-19 pandemic.

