8. CHANGES FROM PROTOCOL-SPECIFIED ANALYSES

Handling of intercurrent events is expanded in this SAP. There are no other changes from the protocol-specified analyses.

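### The SAP adds a completion condition to the per-protocol set and keeps only an observed-case per-protocol analysis, while Section 8 declares neither difference from the protocol

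*SAP*

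**What the plan says.** **Population.** Protocol 9.5 defines the set by eligibility and the absence of relevant violations: "The Per Protocol (PP) Population includes all ITT subjects who meet all inclusion/exclusion criteria and have no protocol violations that affect proper administration" of treatment or accurate evaluation of effectiveness. SAP 5.3 repeats those conditions and inserts one more, that subjects must "complete part 1 of the study, and have no protocol violations" of that kind. SAP 6.2 shows what completion means: "completed Part I (i.e., attended Week 16 visit".

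**Analyses.** Protocol 9.8, under sensitivity analyses, first says that "the primary and key secondary endpoints analyses will also be performed using the per protocol (PP) population". It then lists additional sensitivity analyses for the primary variable, one of which is "The Per Protocol (PP) Population, using Observed Cases (OC". In the SAP, the only PP efficacy analysis is in 6.9.1.3: "Analysis similar to the primary analysis, but on the Per Protocol population using observed cases only with no imputations".

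**Declared changes.** SAP 8 reports that the handling of intercurrent events was expanded, and then states: "There are no other changes from the protocol-specified analyses".

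**Primary rules.** SAP 6.9.1.1 counts subjects as non-responders if Week 16 or baseline data are missing, if rescue or prohibited medication was taken before Week 16, or if study drug was stopped before Week 16.

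**The concern.** Attending Week 16 happens after randomisation and may depend on treatment. Both documents allow a worsening subject to be discontinued as a treatment failure (protocol 3, SAP 3.1), and SAP 3.1 refers to known mechanism-based adverse events of the drug class. Early leaving is therefore unlikely to be unrelated to response or arm.

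SAP 5.3 calls PP the supportive population for efficacy. If its only analysis omits those who left early, it answers a different question from the primary estimand, and agreement between the two says little about how the primary result depends on protocol adherence. A reader who relies on Section 8 would not know that the PP set and the PP analyses differ from the protocol.

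**Working it through.** **1. The population.** Protocol 9.5 sets two conditions: eligibility, and no relevant violation. SAP 5.3 sets three: the same two, plus completion of Part I. The third is new.

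**2. The analyses.**

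| PP analysis | Protocol 9.8 | SAP 6.9.1.3 |
|---|---|---|
| Primary and key secondary analyses repeated on PP | Planned | No version with imputation |
| Observed cases on PP | Planned as additional, primary variable | Kept; the parent heading 6.9.1 covers both endpoints |

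Listing an observed-case version as additional makes sense only if the analysis before it treats missing data differently. That in turn requires PP members with missing Week 16 data. The protocol definition allows them; the SAP definition largely removes them.

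**3. The change statement.** A new condition on a population and the loss of one of two PP analyses are not intercurrent-event handling, so SAP 8 does not cover them. One further undeclared PP difference points the same way: protocol 9.6 summarises baseline characteristics for ITT, PP and Safety, SAP 6.3 for ITT only.

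**4. Who is lost.**
- Left before the Week 16 visit: fails the completion condition and has no Week 16 value, so is absent on both counts.
- Stopped drug but attended Week 16: meets the completion condition. Exclusion depends on the separate Protocol Deviations Specification (SAP 6.7).

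**5. Size.** The visible text gives no PP response or dropout rates, so there is no planned figure to reproduce. What follows is an illustration.

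Assumptions: response among completers pA = 40% (active) and pP = 20% (placebo); dropout before Week 16 is dA and dP; early leavers have no other PP-excluding violation.

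- Completers only: pA − pP = 0.40 − 0.20 = 0.20.
- Early leavers kept as non-responders: pA(1 − dA) − pP(1 − dP).
- Gap, completers minus kept: pA·dA − pP·dP.

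| dA (active) | dP (placebo) | Early leavers kept | Completers | Gap |
|---|---|---|---|---|
| 30% | 15% | 0.40×0.70 − 0.20×0.85 = 0.28 − 0.17 = 0.11 | 0.20 | +0.09 |
| 20% | 20% | 0.40×0.80 − 0.20×0.80 = 0.32 − 0.16 = 0.16 | 0.20 | +0.04 |
| 10% | 30% | 0.40×0.90 − 0.20×0.70 = 0.36 − 0.14 = 0.22 | 0.20 | −0.02 |

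Under these response rates the gap is zero when 0.40·dA = 0.20·dP, that is, when placebo dropout is twice active dropout. Below that ratio the completers difference is the larger; above it, the smaller.

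A null case: suppose response with leavers counted as non-responders is 18% in both arms, and dropout is 30% active and 10% placebo. Among completers the rates are 0.18/0.70 = 25.7% and 0.18/0.90 = 20.0%, a difference of 5.7 points produced by dropout alone.

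**The case against.** Several points on the other side stand.

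- **The completion clause alone does almost nothing.** A subject who missed Week 16 has no observed Week 16 value and drops out of an observed-case analysis with or without the clause. The protocol itself planned that analysis for the primary variable. The clause matters only together with the absence of a PP analysis that retains such subjects.
- **The visible protocol does not state non-responder rules.** A reader might infer that protocol 9.8 prescribes the SAP 6.9.1.1 rules for PP. It does not say so. Its method sentence is partly redacted, it defers detail to the SAP, and SAP 8 says intercurrent-event handling was expanded later. That the first PP analysis follows the primary missing-data rules is the natural reading, but an inference.
- **Not everyone who stopped is removed.** A reader might infer that every subject who discontinued treatment is missing from the PP result. The documents support this only for those who left before the Week 16 visit.
- **The robustness of the primary result does not rest on PP.** These subjects stay in the primary ITT analysis as non-responders. The worst-case analysis treats them unfavourably to active drug, and the tipping-point analysis (run when the primary result is significant) varies them from 0% to 100% responders. PP carries no alpha.

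What these points do not answer is Section 8. Leaving details to the SAP allows the SAP to elaborate; it does not make the statement that nothing else changed correct.

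**Conclusion.** The concern holds as a discrepancy between the documents that affects a supportive result. The PP definition and the set of PP analyses both differ from the protocol, and the SAP's change section is wrong to say otherwise. Early leavers contribute nothing to the only PP estimate.

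In the illustration that estimate is 9 or 4 points higher, or 2 points lower, than one that keeps early leavers as non-responders, depending on the balance of dropout. These sizes rest entirely on assumed response and dropout rates and on early leavers having no other excluding violation. Part of each gap reflects a different estimand rather than error.

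A reader might infer that the PP result is bound to favour the drug, or that the trial's main conclusion is at risk. The documents support neither: the direction depends on which arm loses more subjects, and the primary analysis is untouched. The change is worth making because it is cheap, restores what the protocol most naturally promises, and corrects an inaccurate statement.

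**What to change.** 1. In SAP 5.3, restore the protocol 9.5 definition by removing the completion condition. Check that the Protocol Deviations Specification does not bring it back by classing early leaving or a missed Week 16 visit as an excluding deviation.
2. In SAP 6.9.1.3, run PP for both endpoints under the missing-data and intercurrent-event rules of 6.9.1.1, and keep observed cases as a second PP analysis. Steps 1 and 2 are needed together; step 1 alone would change almost nothing.
3. For the observed-case run, state whether dispensing with imputation also suspends the non-responder rule for PP members who took rescue or prohibited medication, or who stopped drug but attended Week 16. The text leaves this open.
4. In SAP 8, list and justify any PP difference that remains, including the baseline summaries if these stay ITT-only.

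The cost is SAP wording and one extra run of the existing primary-analysis program. The supportive PP estimate may become less favourable.
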